### 7.3.1.4. Missing Data on Covariates

Considering the background of the study, missingness is known for the baseline confounders. Among variables listed in Table 4, Body Mass index (BMI), Race, Ethnicity, SDI and SLEDAI 2000 score are reported with missing values. The rules below will apply:

- The missing data for individual variables will be coded into a “missing” category for categorical variables to allow all subjects to be used in the analysis; for continuous measures, missing data will be set to a fixed value (i.e. median) and an indicator variable will be added in the model.
- However, in the case of very few missing cases ( $<10$ ):
  - The modal category will be assumed for categorical variables.
  - The indicator variable will be omitted from the model for continuous variables
- Specific case of baseline SLEDAI 2000 (S2K composite score):

The Assessments of SLEDAI 2000 score consist of 24 individual items (see section 9.5.5) in which signs and symptoms, laboratory tests, and physician’s assessment for each of 9 organ systems are given a weighted score and summed if present (marked ‘Yes’).

  - A “Clinical SLEDAI 2000 score” (CS2K) will be computed considering all items except “Low Complement” and “Increased DNA Binding”. The CS2K is computed based on the remaining 22 items, with either “absent” or “not done” being regarded as 0.
  - A corresponding variable “total not-done points” calculating the sum of not done weights is also included in the model. "Total not done points" = 0 for subjects who were assessed for all items. "Total not done points" = 18 for subjects with maximum (6) not done items. The variable’s inclusion is to allow the model to differentiate between subjects who have scored x points/101 available compared to subjects who have score x points/83 available, or anywhere in between.
- If the SLEDAI 2000 form is completely missing, then median CS2K (based on subjects who answered  $>0$  questions) and median “total not done points” will be assumed, and an indicator variable will be added in the model.

### 7.3.1.5. Incidence and event rate analysis

Weighted incidence rate per 100 person-years and weighted event rate per 100 person years will be presented for 'ITT' and 'While-On-Initial Exposure' treatment strategies. The 95% CI for the rates will be calculated assuming an exact Poisson distribution method.

Incidence rates will be calculated as total weighted incidence divided by total weighted subject years at risk with corresponding weighted exact Poisson CI:

$$\text{Lower} = \frac{(\text{quantile}('CHISQ', 0.025, 2 * \sum \text{weight} * \text{subject with at least one event})/2)}{\sum \text{weight} * \text{subject years at risk}}$$

$$\text{Upper} = \frac{(\text{quantile}('CHISQ', 0.975, 2 * (\sum \text{weight} * \text{subject with at least one event} + 1))/2)}{\sum \text{weight} * \text{subject years at risk}}$$

Event rates will be calculated as total weighted number of events divided by total weighted follow up time. with corresponding weighted exact Poisson CI:

$$\text{Lower} = \frac{(\text{quantile}('CHISQ', 0.025, 2 * \sum \text{weight} * \text{events}) /2)}{\sum \text{weight} * \text{subject years of follow-up}}$$

$$\text{Upper} = \frac{(\text{quantile}('CHISQ', 0.975, 2 * (\sum \text{events} + 1))/2)}{\sum \text{weight} * \text{subject years of follow-up}}$$

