##### **First step of analysis: Inverse probability of treatment weighting (IPTW)**

Propensity scores will be computed as the probability of being exposed to Benlysta at enrollment given an individual’s baseline characteristics. Logistic regression will be used to derive the PS. Non-stabilized weights (i.e. IPTW) for each individual will be calculated as the inverse of the probability of receiving the actual exposure:  $1/PS$  for the Benlysta arm and  $1/(1-PS)$  for the Non-Benlysta arm.

Inverse probability of treatment weighting (IPTW) (Rosenbaum, 1983) will be used to adjust for differences in covariates balance between exposure groups, Benlysta versus Non-Benlysta. To reduce likelihood of extreme weights being assigned in the analysis, stabilized weights will be computed by multiplying the non-stabilized weight of each individual by the proportion of subjects who were exposed to Benlysta at enrollment :  $p/PS$  for the Benlysta arm and  $(1-p)/(1-PS)$  for the Non-Benlysta arm., (Chesnaye, 2021). For the remainder of the document, references to “weight” refer to stabilized weights.

These weights will create a *pseudopopulation* whereby confounding factors are balanced among Benlysta and non-Benlysta arms. The weights’ distributions will be checked to identify extreme weights which might impact results (see section 7.3.1.3). If the balance assessment reveals that adequate balance cannot be achieved between the Benlysta and non-Benlysta arms (section 7.3.1.2.2), no further analysis using propensity scores will be conducted.

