##### **Second step of analysis: Outcome analysis**

The primary outcome model will be a weighted Poisson regression based on stabilized weights. Weighted incidence rates and event rates will be calculated and presented. Further details presented in section 7.3.1.5.

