### 7.3.1.3. Handling of Extreme Weights

Following satisfaction of positivity assumptions as per section 7.3.1.1.2, if there is evidence of extreme weights ( $> 10$ ) that cannot be resolved by adjusting the PS model then subjects in the tails of the propensity score distributions will have their propensity score truncated at the 99th percentile value (i.e.: large weight will be replaced with the 99th percentile).

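### The intervals for the propensity-weighted rates treat a sum of weights as a Poisson count, so they ignore weight variability and are in general too narrow when weights vary

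*SAP*

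**What the plan says.** SAP 7.3.1 derives stabilized weights, p/PS for BENLYSTA and (1−p)/(1−PS) for the comparator. The purpose given is: "To reduce likelihood of extreme weights being assigned in the analysis, stabilized weights will be computed". The next step states: "The primary outcome model will be a weighted Poisson regression based on stabilized weights". No variance estimator is named there.

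SAP 7.3.1.5 then settles the interval: "The 95% CI for the rates will be calculated assuming an exact Poisson distribution method". For incidence it adds: "Incidence rates will be calculated as total weighted incidence divided by total weighted subject years at risk with corresponding weighted exact Poisson CI". Four limits are printed, each divided by weighted person-years:

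- Incidence, lower: half the 2.5% chi-square quantile on 2Σ(w × patient with an event) degrees of freedom.
- Incidence, upper: half the 97.5% quantile on 2(Σ(w × patient with an event) + 1).
- Event rate, lower: the same form with Σ(w × events).
- Event rate, upper: the form with Σ(events) + 1, without the weight.

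SAP 7.3.1.3 truncates at the 99th percentile "if there is evidence of extreme weights" above 10 that adjusting the propensity model cannot resolve. SAP 2.4 says the intervals are there to convey random error and are not for testing.

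**The concern.** The chi-square limits are exact for a Poisson count, whose variance equals its mean. A sum of weights over event patients is not such a count. One patient with weight 8 moves the rate as much as eight patients with weight 1, yet the formula credits that patient with the information of eight.

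Stabilizing does not help. Within an arm it multiplies every weight by one constant and leaves the relative spread unchanged. It brings the mean weight to about 1, so the weighted sum stays near the raw event count and the interval keeps roughly its unweighted width. The precision lost by weighting does not show.

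At stake are Tables 54.010 and 54.020. They hold the only planned confounding-adjusted rates for the primary safety endpoints, and Section 7.3 gives no other measure of uncertainty for those rates.

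**Working it through.** **Inputs.** From the protocol (Section 8.2, Table 8-1): 2,000 and 1,000 patients, so p ≈ 2/3; 10% annual drop-out; 5 years; 7,773 and 3,886 patient-years (PY); reference rates per 100 PY of 0.68 (death), 5.80 (serious infection) and 0.136 (opportunistic infection). The spread of the propensity score is not in the documents and is assumed throughout.

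**Reproducing the plan's figures.** N(1−0.9⁵)/(−ln 0.9) gives 7,773.5 and 3,886.8 PY. For deaths, 1.96 × √[0.0068 × (1/7,773 + 1/3,886)] = 0.32 per 100 PY, as stated. These figures are unweighted. With every weight equal to 1, the SAP incidence formula is the ordinary exact Poisson interval: 26.4 expected comparator deaths give 0.446–0.993 per 100 PY.

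**Illustration with hypothetical weights.** Take 26 comparator deaths of weight 1, or 20 of weight 0.9 plus one of weight 8. Both sum to 26. Over 3,886 weighted PY the SAP prints 0.44–0.98 for both. In the second case Σw² = 20 × 0.81 + 64 = 80.2. The approximate half-width is then 1.96√80.2/38.86 = 0.45 per 100 PY, against 1.96√26/38.86 = 0.26. The truncation rule does not act, because 8 is below 10. With p = 2/3 a comparator weight passes 10 only when PS exceeds 1 − (1/3)/10 = 0.967.

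**Size of the error.** Let DE = Σw²d / Σwd over event patients (d = 1 for an event). The correct width is about √DE times the SAP width. If risk is unrelated to the score, the large-sample DE is the population mean of (1−p)/(1−PS) for the comparator and of p/PS for BENLYSTA:

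| Logit SD | c-statistic | DE comparator | DE BENLYSTA |
|---|---|---|---|
| 0.25 | 0.57 | 1.03 | 1.01 |
| 0.50 | 0.64 | 1.12 | 1.03 |
| 0.75 | 0.69 | 1.30 | 1.07 |
| 1.00 | 0.74 | 1.60 | 1.14 |
| 1.25 | 0.78 | 2.13 | 1.26 |

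For comparator mortality, using an effective count of 26.4/DE:

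| DE | 95% interval per 100 PY | Width |
|---|---|---|
| 1.0 (SAP) | 0.446–0.993 | 0.547 |
| 1.1 | 0.436–1.012 | 0.576 |
| 1.5 | 0.400–1.080 | 0.680 |
| 2.0 | 0.364–1.158 | 0.794 |

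At DE 1.5 the interval should be 0.680/0.547 = 1.24 times as wide.

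**Coverage by simulation.** 3,000 patients, estimated logistic score, stabilized weights, truncation when a weight exceeds 10, 10% annual drop-out, 1,500 registries per setting. SAP comparator interval, nominal 95%, for serious infection / death / opportunistic infection:

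| Setting | c = 0.64 | c = 0.74 | c = 0.78 |
|---|---|---|---|
| Risk unrelated to score | 93.9 / 94.5 / 96.1 | 90.4 / 89.9 / 94.1 | 89.3 / 89.4 / 92.1 |
| Higher risk more often on BENLYSTA | 93.4 / 92.7 / 93.9 | 85.1 / 82.8 / 88.5 | 80.3 / 83.3 / 87.9 |
| Higher risk less often on BENLYSTA | 95.5 / 96.8 / 97.3 | 94.0 / 94.3 / 96.4 | not run |

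In the last row at c = 0.74 the shortfall moves to BENLYSTA: 91.7 / 91.0 / 91.9%.

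A further simulation, also with truncation, used logit SDs of 0.8 to 1.2. Comparator coverage was 88–94% with risk unrelated to the score and 77–87% when hazard doubles per SD, against 89–96% for a robust interval. With higher-risk patients in the comparator, BENLYSTA coverage at SD 1.2 was 86.5–91%.

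**Event-rate upper limit.** The lower limit and the rate itself use Σ(w × events), but the printed upper limit uses Σ(events). For 225 events (5.80 × 38.86 = 225.4, treating the reference rate as an event rate), half the 97.5% quantile on 452 degrees of freedom is 256.4, and 256.4/225 = 1.14. If the mean weight per event exceeded 1.14, the upper limit would fall below the rate it belongs to.

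**The case against.** **The intervals are descriptive.** SAP 2.4 and 5.7 exclude formal testing, and the weighted rates themselves are unaffected. Both statements are correct, and they lower the severity. They do not excuse the formula, since conveying random error is the one job these intervals have.

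**A reader might infer that the comparator interval is always too narrow and the BENLYSTA interval always sound.** The documents do not support this. They warn of confounding (protocol 1.3 and 10) without saying in which arm the higher-risk patients sit. If they sit in the comparator, comparator coverage is near nominal and BENLYSTA falls short.

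**The SAP has safeguards.** It investigates and truncates weights above 10, and it drops the propensity analysis if balance fails. Truncation does raise coverage: at SD 1.2 with risk unrelated to the score, one run gave 90.0–92.4% with it, against 85–87% in a simulation with no stated truncation. When hazard doubles per SD a shortfall remains (75.9–86.5% in that run). Part of it may be truncation bias, because the robust interval also fell, to 88.6–93.3%.

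**Sparse endpoints are partly protected.** At about five expected events the conservatism of the exact method offsets some of the error. A log-scale sandwich is not a full answer there: it covered as little as about 89% at 0.136 per 100 PY, and it is undefined with zero events.

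**The information is not wholly hidden.** Tables 24.110 and 24.120 give actual event counts, and Tables 53.031 and 53.032 give the weight distributions. This stands, but none of these tables corrects the printed interval.

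**The weighted Poisson regression might be read as implying a robust interval.** SAP 7.3.1.5 specifies exact Poisson limits instead, and Appendix 10 contains no outcome code.

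**Conclusion.** The defect follows from the SAP text alone: the incidence limits carry no term for weight variability. The direction is a general tendency. Intervals are too narrow when weights vary, usually most in the smaller comparator arm, but in the BENLYSTA arm under the opposite channelling.

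The size rests on assumed propensity separation. At logit SD 0.4 it is negligible to small. At 0.8 to 1.2, coverage in the affected arm is about 77–94%, with the SAP's truncation applied. The documents cannot narrow this range.

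The event-rate limits have the same defect, and they also treat repeat events in one patient as independent. The unweighted count in their upper limit is inconsistent with the lower limit. It may be a typing slip, but as printed it would be programmed. Severity: should fix.

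**What to change.** Replace all four formulas in SAP 7.3.1.5 with one of the following:

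- Patient-level robust (sandwich) intervals on the log rate from the weighted Poisson model that SAP 7.3.1 already names, with a log person-years offset. For incidence, the standard error of the log rate is √Σ[w²(d − r·t)²] / Σ(w·d), where r is the weighted rate and t the person-years. For event rates, d is the patient's event total, which also handles recurrence.
- A patient-level bootstrap that refits the propensity model in each resample.

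For sparse endpoints (for example opportunistic infection, malignancy and NMSC), specify a weighted-sum gamma interval based on Σw², with a stated rule for zero events. It held at least 95.6% coverage in the simulations, but it is wide. In one setting at 0.136 per 100 PY (c = 0.74, higher-risk patients less often on BENLYSTA), the comparator width was 0.70 against 0.26 from the SAP formula. State in advance which endpoints use it, or the event count below which it applies.

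Print the actual number of events and the effective sample size, (Σw)²/Σw², beside each weighted rate in Tables 54.010 and 54.020.

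The cost is SAP wording and a few lines of code, to be settled before the weighted outcome tables are run. Some intervals will become wider.

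### The upper confidence limit for the weighted event rate omits the weight from the event count, so it can fall below the estimate it is meant to bound

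*SAP*

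**What the plan says.** SAP section 7.3.1.5 defines the adjusted event rate: "Event rates will be calculated as total weighted number of events divided by total weighted follow up time". It describes the interval this way: "The 95% CI for the rates will be calculated assuming an exact Poisson distribution method". Section 7.3.1 adds that from there on "references to “weight” refer to stabilized weights".

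Four limits are then printed. The count inside the chi-square quantile is:

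| Limit | Count used | Weighted? |
|---|---|---|
| Incidence rate, lower | weighted subjects with an event | yes |
| Incidence rate, upper | "quantile}('CHISQ', 0.975, 2 * (\sum \text{weight} * \text{subject with at least one event} + 1))/2" | yes |
| Event rate, lower | "quantile}('CHISQ', 0.025, 2 * \sum \text{weight} * \text{events}) /2" | yes |
| Event rate, upper | "quantile}('CHISQ', 0.975, 2 * (\sum \text{events} + 1))/2" | **no** |

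All four are divided by weighted person-time. With its denominator, the event-rate upper limit reads "quantile}('CHISQ', 0.975, 2 * (\sum \text{events} + 1))/2)}{\sum \text{weight} * \text{subject years of follow-up".

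The table in SAP section 7.3.3 marks the weighted event rate as a primary analysis alongside the weighted incidence rate. Section 7.1.2 asks for an event rate for every AESI category except mortality. Judging by their titles, Tables 54.010 (ITT) and 54.020 (While On Initial Exposure) carry these results.

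**The concern.** A confidence interval should be built on the same quantity as its point estimate. Here the estimate and lower limit follow the weighted count and the upper limit follows the crude count. Stabilized weights average about 1 over the subjects in an arm, but not over the events. If patients with many events tend to have large weights, the weighted count rises and the upper limit does not follow.

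The SAP tests no hypotheses, so the interval is the reader's only measure of random error around an adjusted rate. In a safety registry the upper limit is the part that matters most, because it states the highest rate still compatible with the data. An upper limit that is too low understates that rate in the arm where weighting raises the event count. The opposite error widens the interval for no reason.

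**Working it through.** **Notation.** E is the crude event count, W the sum of weight × events, and D the weighted follow-up. The SAP's quantile expressions are:

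- L(x) = chi2inv(0.025, 2x)/2
- U(x) = chi2inv(0.975, 2(x + 1))/2

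The estimate is W/D, the lower limit L(W)/D, the printed upper limit U(E)/D and the consistent upper limit U(W)/D. If all weights equal 1, then W = E and the two upper limits agree.

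**Condition for failure.** D cancels. The printed upper limit lies below the estimate exactly when W/E > U(E)/E. It lies below the lower limit when L(W) > U(E).

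**Inputs.** The SAP gives no numerical weighted interval to reproduce, so event counts are assumed from protocol section 8.2 (Table 8-1). Its planning figures check out:

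- 2,000 × (1 − 0.9^5)/(−ln 0.9) = 7,773.5 patient-years, as stated. Half of that gives the comparison cohort's 3,886.
- 1.96 × √(0.058 × (1/7,773 + 1/3,886)) × 100 = 0.927, the stated ±0.93 for serious infection.

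Reference rate × patient-years gives, for serious infection, 0.0580 × 7,773 = 451 events (BENLYSTA) and 0.0580 × 3,886 = 225 (comparison). The other endpoints follow the same way.

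**Thresholds.** The last column is the ratio W/E above which the printed upper limit falls below the estimate.

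| Endpoint | Cohort | E | U(E) | U(E)/E |
|---|---|---|---|---|
| Serious infection | BENLYSTA | 451 | 494.61 | 1.097 |
| Serious infection | comparison | 225 | 256.40 | 1.140 |
| Serious psychiatric | BENLYSTA | 32 | 45.17 | 1.41 |
| Serious psychiatric | comparison | 16 | 25.98 | 1.62 |
| Malignancy excl. NMSC; NMSC (same rate) | BENLYSTA | 18 | 28.45 | 1.58 |
| Malignancy excl. NMSC; NMSC (same rate) | comparison | 9 | 17.08 | 1.90 |
| Opportunistic infection | BENLYSTA | 11 | 19.68 | 1.79 |
| Opportunistic infection | comparison | 5 | 11.67 | 2.33 |

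For serious infection the printed upper limit also falls below the lower limit once W/E exceeds 1.195 (BENLYSTA) or 1.283 (comparison).

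**Worked cases, serious infection, per 100 patient-years.** D is held at the planned patient-years.

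| Cohort | W/E | Estimate | Lower | Upper as printed | Upper with weight |
|---|---|---|---|---|---|
| BENLYSTA | 0.8 | 4.64 | 4.18 | 6.36 | 5.15 |
| BENLYSTA | 1.0 | 5.80 | 5.28 | 6.36 | 6.36 |
| BENLYSTA | 1.1 | 6.38 | 5.83 | 6.36 | 6.97 |
| BENLYSTA | 1.2 | 6.96 | 6.39 | 6.36 | 7.57 |
| comparison | 0.8 | 4.63 | 3.98 | 6.60 | 5.36 |
| comparison | 1.2 | 6.95 | 6.14 | 6.60 | 7.83 |

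The printed upper limit does not move with W/E. On the count scale, the comparison row at 1.2 is W = 270: printed limits 238.8 to 256.4, corrected 238.8 to 304.2. At 0.8 it is W = 180: printed upper 256.4, corrected 208.3.

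**Is such a ratio plausible?** An illustrative simulation assumed 3,000 subjects, one normal confounder, 5.8 events per 100 patient-years, the planned drop-out, and stabilized weights averaging 1.00 per arm, with 400 runs per setting.

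- No link between confounder and event rate: the printed limit was below the estimate in about 0% of runs.
- Log-odds slope 0.5 for treatment and log-rate slope 0.5 for events: W/E averaged 1.18 in the comparison arm and the limit was below the estimate in 68% of runs.
- Treatment slope raised to 0.8: 94% of comparison-arm runs, with upper below lower in 32%.
- Treatment slope 0.5 and event slope −0.5: the BENLYSTA arm was affected, in 29% of runs.

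**The case against.** The best reply is that this is a slip whose intent is obvious. The definition of the rate, the description of the interval and the parallel incidence formula all show what was meant, and a limit below its estimate would be noticed in the output. Intent is indeed clear, but a programmer and a validator who both follow the SAP would produce the same wrong number. Only the extreme cases are visible; a limit that is merely too high or too low looks normal.

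Second, the reach is limited. Weighted incidence rates, lower limits, point estimates and all unweighted intervals are unaffected. Comparisons are descriptive, the text of section 7.3.3 puts weighted incidence first, and the weighted analysis is dropped if balance is not achieved. All of this stands, although the table in section 7.3.3 still labels the weighted event rate primary.

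Third, the illustration uses the most frequent endpoint in the protocol's table. This is fair: for rarer endpoints a limit below the estimate needs a ratio of 1.4 or more. The SAP does tolerate large individual weights, since truncation applies only "if there is evidence of extreme weights ( $> 10$ ) that cannot be resolved by adjusting the PS model".

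Fourth, the driver is the count ratio W/E, not the movement of the rate. With E = 225 over 3,886 patient-years (5.79 per 100), W = 270 and weighted follow-up 4,800, the rate falls to 270/4,800 = 5.63, yet the printed upper limit of 256.4/4,800 = 5.34 is still too low. This refines the statement of direction but does not remove the error.

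Finally, the formula was read from a PDF by a program, so a lost term is possible. The other three formulas kept theirs.

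**Conclusion.** The point holds: the event-rate upper limit in SAP section 7.3.1.5 is wrong as printed. It is correct only when the weighted and crude event counts coincide, too low when the weighted count is larger and too high when it is smaller. It falls below the estimate at count ratios of about 1.10 to 1.14 for serious infections and about 1.4 to 2.3 for the rarer endpoints tabulated above.

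The algebra needs no assumptions. The sizes rest on event counts taken as reference rate × planned patient-years, weighted follow-up equal to planned follow-up, and assumed values of W/E. The protocol does not say whether its reference rates count first or all events. The placement in Tables 54.010 and 54.020 is inferred from their titles, because the mock shells are in a separate file.

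**What to change.** In the event-rate upper limit of SAP section 7.3.1.5, replace the plain event sum with the sum of weight × events, keeping the + 1 and the weighted denominator. First check the SAP's source file, and check that the SAS code matches the corrected formula. Add a program check that lower ≤ estimate ≤ upper, and test with unequal weights: a test with all weights equal to 1 passes under either formula.

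The cost is one term in the SAP and one line of code, made before the weighted tables are run. No new data are needed and nothing is lost. The change restores consistency only. Whether a chi-square Poisson interval on a weighted count has correct coverage is a separate question; if another variance method replaces this closed form, the correction is no longer needed.
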